Using this approach, it is expected to address the informatics challenge of determining how to design information technology that improves engagement and clinical outcomes for patients who require continuous monitoring and who engage an informal caregiver in self-management outside clinical settings. Our work extends the design of remote-monitoring systems from stationary, home-based systems to wearable devices that patients can engage with throughout an active day in the community. Our research team—which consists in a biomedical systems engineer, a human factors engineer specialized in consumer health informatics, a pediatric endocrinologist, and a pediatrician specialized in clinical research — works in alliance with the Center for Diabetes Technology at the University of Virginia. Study team members have developed this ambulatory platform that will be used as the foundation for this study.

Rationale: The hypothesis of this study is that individuals randomized to the CGM/Fitbit with no weekly feedback (Control Group) will improve management modestly initially (as a result of either of new access to CGM or the Hawthorne effect of being studied), but their measures of engagement (patient self-management behavior (i.e. personal insulin parameters) and diabetes-related dyad communication) will return to baseline levels by the 12-week evaluation. By contrast, it is hypothesize that individuals randomized to CloudConnect (Experimental Group) will have a greater increase in engagement and dyad communication by 8 weeks that is sustained by 12 weeks (3 months).

It is further hypothesize that adolescents randomized to CloudConnect will have a lowering of HbA1c that is related to the increase in dyad disease-specific engagement. Moreover, our hypotheses are that this unique self-management approach in T1D will increase engagement of adolescents and their informal caregiver through increased communication and self-management behavior, and that this increase in engagement will lead to improved medical outcomes.

These hypotheses are based on data from preliminary studies collected by the study group and the literature. This preliminary data support that parents of adolescents with T1D are eager to follow their child's blood

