Study Objectives & Endpoint Definitions:

As mentioned previously, this project seeks to assess how CloudConnect affects participant engagement, dyad engagement, and clinical outcomes in adolescent T1D.

We will assess how adolescents and their parent(s)/guardian(s) respond to this new approach using the Family Communication Inventory (FCI). This diabetes-specific approach was designed by the investigators to assess parent-child communication regarding tasks (discussion of insulin dosing for a given meal, BG trends, need for dose changes). As an outcome measure, scores for parents and adolescents are summed, with higher scores representing higher degree of engagement and T1D-specific communication.

Power/Precision of the study to address major study endpoints:

In using the FCI, we determined based on preliminary data from 220 adolescent/parent participants eligible for the study, with mean (90.3) and standard deviation (12.5) that we are powered to detect a difference of 8.5% in this outcome in the treatment group with 80% power and an alpha of 0.05. This study will require 40 adolescent participants with 40 parent(s)/guardian(s) to complete per arm. Assuming a non-adherence/drop-out rate of 20-30% for Intention-to-Treat (ITT) analysis, 55 participants is yielded per arm.

3. Provide a justification for the sample size used in this protocol.

The study team will attempt to enroll an equal number subjects based on gender, CSII, and MDI use. The study is powered to detect a difference of 8.5% in this outcome in the treatment group with 80% power and an alpha of 0.05. This study will require 40 adolescent participants with 40 parent(s)/guardian(s) to complete per arm. Assuming a non-adherence/drop-out rate of 20-30% for Intention-to-Treat (ITT) analysis, 55 participants is yielded per arm.

4. What is your plan for primary variable analysis?

Because this is a randomized study, our primary outcome (score on the Family Communication Inventory) will be by t-test comparing those randomized to CloudConnect to usual care+CGM. Comparison of secondary outcomes between treatment groups will also be t-tests. Secondary analyses of both the primary and secondary outcomes will utilize multivariable ANOVA, particularly in the event that key variables differ between groups. For example, if average steps per day [as a measure of exercise] is higher in one group vs.

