Both groups will participate in the same number of visits (completed either in clinic or via phone or video conferencing) and follow up communication contacts done by phone calls, text messages and/or emails during the entire length of the trial. The production of the CloudConnect Report, in combination with the available Dexcom alarms and apps, is the study differential between groups.

*Secondary health outcomes: Average Blood Glucose values by Continuous Glucose Monitor; average total daily insulin; average carbohydrate of grams entered; number of insulin boluses; average number of steps by day

Figure 1: Study Design

There are four visits in the Main Study. Visit 1 and 2 may be combined and may be in person or via phone or video conference. A repeat Hemoglobin A1c will be collected if visit 1 and 2 are greater than 28 days. Visit 3 may be completed by phone. In addition, there will be weekly communication done by phone call, text message and/or email throughout the entire 12 weeks (3 months) of the data collection portion of the study. Method of weekly communications with the adolescent and parent will be based on participant/parent preference. The study team will communicate separately with the child and the parent in order to obtain their feedback independent of the other.

Subjects will be asked to electronically complete the following questionnaires at the completion of Visit 1 and repeated again at the conclusion of their study participation. Questionnaires may be answered remotely (i.e. at home) within a week of the visit or during a CRU visit.

- Blood Glucose Monitoring Communication questionnaire (Hood et al Diab Care 2004)
- Child and Parental Responsibility Questionnaire (adapted from Anderson et al J. Ped Psychol 1990)
- Child Self-Management
- Diabetes Care and Communication
- Diabetes Family Conflict Scale-Revised (Hood et al Diab Care 2007)
- Family Communication Inventory

- MY-Q (deWit et al Ped Diab 2012)
- Questions about CloudConnect use (CloudConnect group only, asked only at study end):
 - On a scale of 1-7, with 1 being very difficult and 7 being very easy, how easy was it to understand the information provided in the weekly reports? Can you tell me why you gave the score you did? What could have made the weekly reports easier to understand?

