Visit 2 (may be combined with Visit 1, may be done via phone or video): Adolescent subjects will be randomized and trained on the use of the study CGM and Fitbit. The CGM will be inserted into their abdomen per manufacturer instructions. Both Control and Experimental Group subjects will use their own personal pump. If the subject uses multiple daily injections (MDI), a commercially available Bluetooth connected insulin pen (inPen) will be given to both the Control and Experimental subjects in order to be able to collect the data accurately about meal time bolus treatments. Both pump users and MDI subjects will use their personal insulin. Each group will provide the study team weekly downloads from the study equipment and the personal insulin pump. Weekly CloudConnect reports will be provided to the Experimental Group participants *only*.

Depending on the subjects/family preference, the study team contact subjects via phone calls, text messages and/or emails at least once a week during the trial to:

- a) Remind them to download and transmit the data
- b) Check for AEs or SAEs
- c) Ask weekly standardized questions

All subjects will be reminded on how to download study data, if necessary. Both groups may complete a 1-week run-in period if they are CGM-naïve to ensure they are comfortable with the use of the study equipment, that all the study devices work properly, and to address issues related to transmission of the data to the study team. This run-in period may be repeated as necessary up to 3 times at the request of the study subject or study team. This data will not be included as part of the 12 week data collection. For subjects who have CGM experience, the investigator will determine if it is appropriate for he or she to skip the run-in period.

Visit 3 Check-in (Week 8 / on-site, email, or phone):

Subjects will download diabetes equipment weekly and submit the data to the study team for 12 weeks. Subjects may be asked to repeat a week of data collection if the quality of the data is insufficient for analysis.

A Check-In with the adolescent and parent/guardian will be completed to evaluate compliance and to answer any questions that the adolescent or parent may have about the study.

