Visit 4 – End of Study (about Week 12): Subjects will be asked to return to the Clinical Research Unit (CRU) to return study equipment (i.e. Bluetooth pen, CGM, Fitbit), if possible. A post-study HbA1c test will be obtained with a point-of-care equipment or local laboratory (same method as screening collection). This can be omitted if it is not possible to go to a laboratory or come to the clinic because of governmental restrictions such as Stay-at-Home orders. Questionnaires will be completed electronically at the end of this visit. Questionnaires may be completed at home prior to this visit or at the CRU.

2. If this protocol involves study treatment, explain how a subject will be transitioned from study treatment when they have completed their participation in the study.

The study intervention is to evaluate the communication between the adolescent study subjects and their parents. The treatment for T1D is subcutaneous insulin either by using insulin pumps or insulin pens. This

treatment will remain the same at the completion of this study. Subjects will return to using their personal diabetes equipment and follow their own insulin parameters.

Subject Compliance with Study Procedures

- 1. Explain how the study team will monitor the subject for compliance with the study procedures.** A mid-study visit during Week 8 is planned to assess compliance. In addition, there will be at least 1 phone call or text message per week to remind subjects to download and transmit the required data, if needed.

It will be at the discretion of the investigator to determine if the patient is not compliant, i.e. three or more weeks with no data received, and the subject will be withdrawn for the study and replaced.

- 2. Describe criteria for when a subject is considered to be non-compliant with study procedures.**

The subject will be dismissed for the study if the subject misses 3 or more weeks of data downloads.

Bibliography

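### Randomised dyads who miss three weekly downloads are removed and replaced, and nothing in the plan brings them into the intention-to-treat comparison it names

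*Combined protocol and SAP*

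**What the plan says.** Randomisation takes place at Visit 2 (Study Procedures, Main Study): "Adolescent subjects will be randomized and trained on the use of the study CGM and Fitbit". The 12 weeks of weekly downloads follow.

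Subject Compliance with Study Procedures then gives two rules with the same threshold. Item 1 leaves the judgement to the investigator: "three or more weeks with no data received, and the subject will be withdrawn for the study and replaced". Item 2 states no discretion: "The subject will be dismissed for the study if the subject misses 3 or more weeks of data downloads".

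Statistical Considerations, item 2, counts the requirement in completers: "This study will require 40 adolescent participants with 40 parent(s)/guardian(s) to complete per arm". It continues: "Assuming a non-adherence/drop-out rate of 20-30% for Intention-to-Treat (ITT) analysis, 55 participants is yielded per arm". Item 3 repeats both statements, and intention-to-treat is mentioned nowhere else. Item 4 says the primary outcome "will be by t-test comparing those randomized to CloudConnect to usual care+CGM", and then judges baseline imbalance among those who complete.

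The FCI and the other questionnaires are completed at Visit 1 and "repeated again at the conclusion of their study participation". They may be answered at home.

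**The concern.** The rule acts after randomisation and on a behaviour of the dyad. Downloading is not the FCI, and a missed download can be a technical failure. But the parent is asked to send the data each week, so persistent failure to do so is a plausible marker of the engagement the FCI is meant to capture. The trial is open-label and only the CloudConnect arm gets a report built from its downloads, so the incentive to keep downloading may differ by arm.

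If removal does differ by arm, the groups in the t-test are no longer those formed by randomisation. Replacement restores the head count but not the comparability. If downloading and FCI are positively related, heavier loss from the control arm works against CloudConnect and heavier loss from the CloudConnect arm works in its favour.

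**Working it through.** **1. The plan's own figure.** Inputs from Statistical Considerations, item 2: mean 90.3, SD 12.5, difference 8.5%, power 80%, alpha 0.05. I take the test as two-sided and the 8.5% as relative.

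- Difference: 0.085 × 90.3 = 7.68 points.
- n per arm: 2 × 12.5² × (1.960 + 0.842)² / 7.68² = 41.6, so 42. The plan says 40. Power at 40 is 78% by normal approximation (77% by t-test), so the figure is close.
- Inflation: 40/0.80 = 50 and 40/0.70 = 57.1, so 58. The stated 55 implies a loss of 1 − 40/55 = 27.3%.

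So the 80% belongs to 40 completers per arm, and 55 is the number needed to reach them. At 20–30% loss, 55 leaves 44 to 38.5 per arm.

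**2. What a removed dyad contributes.** At most it gives an FCI on leaving, if the end of its participation is read that way. The Rationale predicts that control engagement rises first and then "will return to baseline levels by the 12-week evaluation". On the plan's own hypothesis, an early score cannot stand in for a week-12 score, and no rule says how one would be used.

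**3. Bias if removal depends on engagement.** Assumptions not in the documents: all loss is download-driven; compliance and FCI are jointly normal with correlation ρ of 0.2 to 0.5, the same in both arms; the least compliant fraction p of each arm is removed. The mean of the retained dyads then rises by ρ × 12.5 × φ(z_p)/(1 − p).

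- p = 0.20: 0.280/0.80 = 0.350
- p = 0.30: 0.348/0.70 = 0.497
- 30% removed from control and 20% from CloudConnect: bias = ρ × 12.5 × (0.350 − 0.497), which is −0.37 points at ρ = 0.2 and −0.92 at ρ = 0.5, or 5% and 12% of 7.68.

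The formula contains no n, so replacement leaves the bias unchanged. Simulation (40,000 trials per cell, two-sided t-test, replacement to 40 per arm):

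| Removal, control v CloudConnect | Bias (points) | Result at ρ = 0.2 and 0.5 |
|---|---|---|
| 25% v 25% | 0 | type I error 5%; power 78% and 82% |
| 30% v 20% | −0.4 to −0.9 | type I error 5.2% and 6.4%; power 74% and 72% |
| 20% v 30% | +0.4 to +0.9 | false positives favouring CloudConnect about 3.5% and 5.4%, against 2.5% nominal |

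**4. A harsher case.** Suppose loss is equal at 20–30% but removed dyads score 0.5 to 1 SD lower in one arm only. The bias is 0.20 × 6.25 = 1.25 up to 0.30 × 12.5 = 3.75 points, and type I error at 40 per arm is about 7% to 27%. The documents cannot say which case applies.

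**5. Power when everyone randomised is analysed.** As a pessimistic assumption, removed dyads gain nothing. The difference falls to 7.68 × 0.80 = 6.14 or 7.68 × 0.70 = 5.37 points. Adjusting for baseline FCI with correlation r (assumed) reduces the SD to 12.5 × √(1 − r²). The 105-dyad consent ceiling (Human Participants, item 4) allows about 52 per arm, not 55.

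| Analysis | 55 per arm | 52 per arm |
|---|---|---|
| Unadjusted t-test | 72% to 61% | 70% to 58% |
| Adjusted, r = 0.3 | 76% to 65% | 74% to 62% |
| Adjusted, r = 0.5 | 84% to 73% | 82% to 71% |

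Unadjusted, 80% power would need about 66 to 85 per arm.

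**The case against.** The plan does say that the t-test compares those randomised, and it names intention-to-treat. No sentence states that removed dyads leave the analysis, so the compliant-dyad reading is an inference. That is fair as to intent. But a t-test needs an outcome, and none is planned at week 12 for these dyads, so the stated intent cannot be carried out.

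The bias figures rest on assumptions. The 20–30% covers drop-out and non-adherence together, so treating all of it as download removal is an upper bound. Within that range the bias is at most 12% of the target. In the 30% v 20% case it is conservative: false positives favouring CloudConnect fall to about 2% and 1%. Nothing in the documents makes the opposite split likelier. All of this stands, and it limits the weight the bias figures can carry.

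Both arms have the same rule, visits, weekly reminders, repeat weeks for poor data and week-8 check-in, with a run-in for dyads new to CGM. These should reduce removals, technical ones above all. They do not make removal equal by arm, and they supply no outcome for those removed.

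Items 1 and 2 answer different form questions and share one threshold. The conflict is only over discretion, but it affects who is removed and needs reconciling.

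**Conclusion.** The concern holds. The plan names intention-to-treat but, followed as written, produces a comparison of dyads that kept downloading. That much rests on the text and is firm. The size of any bias is not: it is zero under the null when selection is alike in both arms, under one point for a 30% v 20% split on the assumed correlations, and larger only if removed dyads differ from retained ones in one arm and not the other. The case for acting rests less on these figures than on two facts: the primary comparison is affected, and an outcome not collected at week 12 cannot be obtained afterwards.

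**What to change.** - Separate non-compliance with downloads from withdrawal from outcome follow-up, and reconcile items 1 and 2 on discretion.
- Ask both members of every randomised dyad for the electronic week-12 FCI, and the adolescent for HbA1c where possible, whatever their download record.
- Recruit to a fixed number randomised, and do not substitute new dyads for randomised ones in the primary set.
- Define the primary analysis as all dyads as randomised. Handle missing FCI by multiple imputation or a likelihood model using baseline FCI and the stratification factors, with a delta-adjusted sensitivity analysis.
- Report compliance removals by arm, and keep the compliant-dyad comparison as secondary.
- Restate power for the intention-to-treat comparison.

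The cost is protocol wording and some reminders for a questionnaire that can be answered at home, through weekly contacts that already exist. The real price is dilution. If dyads that stop downloading gain nothing, the stated 80% is not met unadjusted. Under the 105-dyad ceiling, baseline adjustment reaches it only at the lower loss rate and r = 0.5. The change can be made without enlarging the trial, but the sponsor should then either state the lower power or raise the ceiling.
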